3.7. Visit Windows

3.7.1. Definition of Study Day

Study day is the day relative to the date of the first dose of study drug. Study Day 1 will be defined as the day of first dose of study drug administration.

Study day will be calculated from the date of first dose of study drug administration and derived as follows:

- For postdose study days: Assessment Date – First Dose Date + 1
- For days prior to the first dose: Assessment Date – First Dose Date

The last dose date will be the end date on study drug administration eCRF for the record where the “subject permanently discontinued” flag is ‘Yes’.

If there are subjects for whom the date of last study drug is unknown due to the reason that the subject was lost to follow-up and not able to be contacted, the date of last dose will be estimated using the maximum of nonmissing study drug start or stop dates, visit dates and laboratory collection dates (posttreatment visits and unscheduled visits are not included).

3.7.2. Analysis Windows

Subject visits might not occur on protocol-specified days. Therefore, for the purpose of analysis, observations will be assigned to analysis windows.

In general, the baseline value will be the last nonmissing value on or prior to the first dose date of study drug.

HCV RNA, vital signs, and safety laboratory data collected up to the last dose date + 3 days are considered to be on-treatment data and HCV RNA, vital signs and safety laboratory data collected after the last dose date + 3 days are considered posttreatment data. The analysis windows for on-treatment HCV RNA, vital signs and safety laboratory data are provided in [Table 3-1](#).

Table 3-1. Analysis Windows for On-treatment HCV RNA, Vital Signs and Safety Laboratory Data

Nominal Visit	Nominal Day	Lower Limit	Upper Limit
Baseline	1	(none)	1
Week 1	7	2	11
Week 2	14	12	21
Week 4	28	22	35
Week 6	42	36	49
Week 8	56	50	63
Week 10	70	64	77
Week 12	84	78	≥ 85

HCV RNA, vital sign, and safety laboratory data collected after the last dose date + 3 days will be assigned to the posttreatment follow-up (FU) visits. Visit windows will be calculated from the last dose date (ie, FU Day = collection date minus the last dose date) as shown in [Table 3-2](#).

Table 3-2. Analysis Windows for Posttreatment HCV RNA, Vital Signs and Safety Laboratory Data

Nominal FU ^a Visit	HCV RNA			Vital Signs and Safety Laboratory Data ^b		
	Nominal FU Day	Lower Limit	Upper Limit	Nominal FU Day	Lower Limit	Upper Limit
FU-4	28	21	69	28	4	30
FU-12	84	70	146	NA	NA	NA
FU-24	168	147	210	NA	NA	NA

a FU-x visit = posttreatment Week-x follow-up visit.

b Vital signs and safety labs will only be summarized for the FU-4 visit (up to 30 days after last dose).

ECG data collected up to the last dose date + 3 days are considered to be on-treatment data. Qualitative assessments of whether the ECG is normal or abnormal will be assessed for on-treatment data based on the visit windows as shown in [Table 3-3](#).

Table 3-3. Analysis Windows for On-treatment ECG Data

Nominal Visit	Nominal Day	Lower Limit	Upper Limit
Baseline	1	(none)	1
Week 1	7	2	45
Week 12	84	46	(none)

Note: ECGs are to be collected at screening, Day 1, Week 1, and Week 12 or End of Treatment. For purposes of analysis, baseline value will be the last available value prior to the first dose of study drug and end of treatment value will be the last available value on or prior to the last dose date + 3 days.

3.7.3. Selection of Data in the Event of Multiple Records in an Analysis Window

Depending on the statistical analysis method, single values may be required for each analysis window. For example, change from baseline by visit usually requires a single value, whereas a time-to-event analysis would not require 1 value per analysis window.

If multiple valid nonmissing numeric observations exist in an analysis window, records will be chosen based on the following rules if a single value is needed:

- For baseline, the last available record on or prior to the date of the first dose of study drug will be selected. If there are multiple records with the same time or no time recorded on the same day, average (arithmetic mean) will be used for the baseline value. If multiple ECG measurements occur on the same day prior to first dose of any study drug, the average will be used considered as baseline value for continuous data, regardless of the timing of these multiple ECG measurements.

- For postbaseline visits:
 - The record closest to the nominal day for that visit will be selected except for HCV RNA posttreatment follow-up visits, for which the latest record in the analysis window will be selected.
 - If there are 2 records that are equidistant from the nominal day, the later record will be selected.
 - If there is more than 1 record on the selected day, the average will be taken, unless otherwise specified.

If multiple valid nonmissing categorical observations exist in a window, records will be selected as follows:

- For baseline, the last available record on or prior to the date of the first dose of study drug will be selected. If there are multiple records with the same time or no time recorded on the same day, the value with the lowest severity will be selected (eg, normal will be selected over abnormal). If multiple ECG measurements occur on the same day prior to the first dose of any study drug, the value with the lowest severity will be selected regardless of the timing of these multiple ECG measurements.
- For postbaseline visits, follow the same rules described above for postbaseline numeric observations, except that if there are multiple records on the same day, the most conservative value will be selected (eg, abnormal will be selected over normal).

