3.4. Missing Data and Outliers

3.4.1. Missing Data

In general, missing data will not be imputed unless methods for handling missing data are specified.

For missing last dosing date of study drug, imputation rules are described in Section 3.7.1. The handling of missing or incomplete dates for adverse event (AE) onset is described in Section 7.2.5.2, and for prior and concomitant medications in Section 7.5.

For analyses of categorical HCV RNA data, missing posttreatment HCV RNA data will have the missing data imputed. Missing on-treatment HCV RNA will have the missing data imputed up to the time of the last dose (for on-treatment displays). If the study day associated with the last dosing date is greater than or equal to the lower bound of a visit window, and the value at the visit is missing, the value will be imputed. If the study day associated with the last dosing date is less than the lower bound of a visit window then the on-treatment value at that visit will remain missing.

If a HCV RNA data point is missing and is preceded and followed in time by values that are “< LLOQ target not detected (TND)”, then the missing data point will be set to “< LLOQ TND”. If a data point is missing and preceded and followed by values that are “< LLOQ detected”, or preceded by “< LLOQ detected” and followed by “< LLOQ TND”, or preceded by “< LLOQ TND” and followed by “< LLOQ detected”, then the missing value will be set to “< LLOQ detected”. In these situations the data point will be termed a bracketed success; otherwise, the data point will be termed a bracketed failure (ie, \geq LLOQ detected). If a data point is missing and is not bracketed, the missing data point will also be termed a failure (ie, \geq LLOQ detected) except for SVR24, which will be imputed according to SVR12 status. Success for SVR12 who have no further HCV RNA measurements collected will be counted as a success for SVR24 due to the high correlation between these 2 endpoints.

For the analyses of continuous HCV RNA efficacy data, when and only when a missing HCV RNA value is imputed as < LLOQ TND or < LLOQ detected according to the imputation rule described above, the corresponding continuous value will be imputed to LLOQ – 1 IU/mL. No other imputation will be performed for continuous HCV RNA data.

For health-related quality of life data SF-36, missing data will not be imputed.

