4.2.1. Duration of Exposure to Study Drug

Total duration of exposure to study drug will be defined as last dose date minus first dose date plus 1, regardless of any temporary interruptions in study drug administration, and will be expressed in weeks using up to 1 decimal place (eg, 4.8 weeks).

The total duration of exposure to study drug will be summarized using descriptive statistics (n, mean, SD, median, Q1, Q3, minimum, and maximum) and using the number (ie, cumulative counts) and percentage of subjects exposed through the following time periods: baseline (Day 1), Week1 (Day 7), Week 2 (Day 14), Week 4 (Day 28), Week 6 (Day 42), Week 8 (Day 56), Week 10 (Day 70), and Week 12 (Day 84). A 3-day window is applied to the last planned on-treatment visit to match with the protocol-specified visit window, ie, number of subjects exposed through week 12 is calculated as the number of subjects who were exposed to study drug for at least 81 days. Summaries will be provided by region for the Safety Analysis Set.

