Appendix 1. Study Procedures Table
Study Visits

	Screening	Day 1	On-treatment Study Week (± 3 days)							Post treatment Study Week (± 5 days) ⁱ		
			1	2	4	6	8	10	12/ET	4	12	24
Clinical Assessments												
Informed Consent	X											
Determine Eligibility	X	X										
Medical History	X											
Physical Examination	X	X							X			
Height	X											
Weight	X	X							X		X	X
Vital Signs ^b	X	X	X	X	X	X	X	X	X	X	X	X
12-Lead ECG ^c	X	X	X						X			
AEs	X	X	X	X	X	X	X	X	X	X		
Concomitant Medications	X	X	X	X	X	X	X	X	X	X		
Pregnancy Prevention Counseling		X							X	X		
Health Related Quality of Life Survey, SF-36		X							X	X	X	
Review of Study Medication Compliance ^e			X	X	X	X	X	X	X			
Study Drug Dispensing ^a		X			X		X					

	Screening	Day 1	On-treatment Study Week (± 3 days)							Post treatment Study Week (± 5 days) ¹			
			1	2	4	6	8	10	12/ET	4	12	24	
Laboratory Assessments													
Hematology, Chemistry	X	X	X	X	X	X	X	X	X	X	X		
Coagulation Tests	X	X							X				
HCV RNA	X	X	X	X	X	X	X	X	X	X	X	X	X
Viral RNA Sequencing / Phenotyping Sample ^j		X	X	X	X	X	X	X	X	X	X	X	X
Pregnancy Testing ^d	X	X			X		X		X	X			
Urinalysis, Urine Drug Screen	X												
HCV Genotyping, IL28B	X												
HCV, HIV, HBV Serology	X												
HbA1c, Fibrotest [®]	X												
PPD													
Pharmacogenomic Sample ^e		X											
Imaging for Hepatocellular Carcinoma (HCC) ^f	X												

- a Day 1 assessments must be performed prior to dosing.
- b Vital signs include resting blood pressure, pulse, respiratory rate, and temperature.
- c Subjects will be required to rest in a supine position for ≥ 5 minutes prior to making a recording. The investigator (or qualified designee) should review the ECG traces recorded in real time for gross abnormalities.
- d Females of childbearing potential only. Serum β -hCG pregnancy test performed at screening and confirmation of positive urine pregnancy test. All females of childbearing potential will have urine pregnancy testing every 4 weeks during the dosing period. If urine is positive, confirm immediately with serum β -hCG.
- e Only for subjects who have provided consent for this sample and testing. This sample can be obtained at a subsequent visit if not obtained at Day 1.
- f If presence of cirrhosis is determined, then appropriate diagnostic imaging (e.g., CT or ultrasound) should be performed to exclude the presence of hepatocellular carcinoma (HCC)

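### Table 3-1 places Study Day 11 in the Week 1 window, although on the SAP's stated nominal days and ±3-day tolerance it is nearer to Week 2 and is a permitted Week 2 visit day

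*SAP*

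**What the plan says.** Four parts of the SAP bear on this.

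- **Windows.** Section 3.7.2 gives the "analysis windows for on-treatment HCV RNA, vital signs and safety laboratory data" in Table 3-1. Week 1 has nominal Day 7 and limits 2 and 11. Week 2 has nominal Day 14 and limits 12 and 21.
- **Day count and tolerance.** Section 3.7.1 counts the first dose as Day 1: "For postdose study days: Assessment Date – First Dose Date + 1". Section 4.2.1 repeats the pairing of weeks and days, for example "Week 2 (Day 14), Week 4 (Day 28), Week 6 (Day 42"). The visit columns in Appendix 1 are headed "On-treatment Study Week (± 3 days"). Section 4.2.1 shows how three days are taken off a nominal day: "A 3-day window is applied to the last planned on-treatment visit to match with the protocol-specified visit window", so that exposure through Week 12 is the "number of subjects who were exposed to study drug for at least 81 days".
- **Choice among several records.** For on-treatment visits, Section 3.7.3 says: "The record closest to the nominal day for that visit will be selected". If two records are equally distant, the later one is used.
- **Empty visits.** Under Section 3.4.1, if the last dosing day is on or after the lower bound of the window "and the value at the visit is missing, the value will be imputed" for categorical HCV RNA. It becomes < LLOQ if the values before and after are < LLOQ, and otherwise a failure (≥ LLOQ). Continuous HCV RNA is filled in only in the bracketed < LLOQ case.

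**The concern.** A visit made within its permitted range should fall in its own analysis window. On the printed nominal days, a Week 2 visit on Day 11 does not. It goes to Week 1, where the Week 1 record normally displaces it, and Week 2 may be left with nothing.

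The outputs at stake are the Week 2 on-treatment summaries. These are the percentage with HCV RNA < LLOQ by visit and the HCV RNA change from baseline (both secondary endpoints in Section 6.2.1), and the Week 2 laboratory and vital sign summaries. Week 2 is early in treatment, when a subject may pass from ≥ LLOQ to < LLOQ between two visits, so the choice of record can change the category.

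**Working it through.** **Inputs.** Nominal days 7, 14, 28, 42, 56, 70, 84 and the window limits come from Table 3-1. The ±3 days come from Appendix 1. The selection rule is in Section 3.7.3 and the imputation rule in Section 3.4.1.

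**Step 1. Limits against midpoints of the printed nominal days.**

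| Boundary | Midpoint | Printed upper / next lower limit |
|---|---|---|
| Week 1 / 2 | (7+14)/2 = 10.5 | 11 / 12 |
| Week 2 / 4 | (14+28)/2 = 21 | 21 / 22 |
| Week 4 / 6 | (28+42)/2 = 35 | 35 / 36 |
| Week 6 / 8 | (42+56)/2 = 49 | 49 / 50 |
| Week 8 / 10 | (56+70)/2 = 63 | 63 / 64 |
| Week 10 / 12 | (70+84)/2 = 77 | 77 / 78 |

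Five boundaries follow from the midpoint with a tied day going to the earlier visit. The same rule gives 10 / 11 for Week 1 / 2, not 11 / 12. Directly, |11 − 7| = 4 and |11 − 14| = 3. Among Days 2 to 84, Day 11 is the only day assigned to a visit that is not its nearest, ties aside.

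**Step 2. Limits against the visit tolerance.** Section 4.2.1 takes 84 − 3 = 81. Counted the same way, Week 1 runs from 7 − 3 = 4 to 7 + 3 = 10, and Week 2 from 14 − 3 = 11 to 14 + 3 = 17. Checking all seven visits, Day 11 is the only permitted day outside its own window.

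**Step 3. What happens to a Day 11 record.** It competes for the Week 1 slot.

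- Week 1 record on Days 4 to 10: at most 3 days from Day 7, so it always beats Day 11 at 4 days. The Day 11 record enters no single-value by-visit summary.
- Week 1 record on Day 3 (4 days, a tie that goes to the later record), on Day 2 (5 days), or absent: the Day 11 value is reported as Week 1.

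In either case Week 2 is empty unless another record falls on Days 12 to 21.

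**Step 4. What an empty Week 2 becomes.**

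- Laboratory and vital signs: missing.
- Continuous HCV RNA: excluded, unless bracketed by < LLOQ values, when it is set to 15 − 1 = 14 IU/mL.
- Categorical HCV RNA: imputed if the last dose is on or after Day 12. If the Week 1 value is ≥ LLOQ and is taken as the preceding value, the result is a failure, even when the Day 11 measurement was < LLOQ. If the values on both sides are < LLOQ, the result is < LLOQ and no false failure arises.

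**Step 5. Illustration of frequency (assumption only).** The SAP gives no data on visit scatter. For on-time Week 2 visits spread normally around Day 14, rounded to whole days and limited to Days 11 to 17, the Day 11 share is [Φ(−2.5/SD) − Φ(−3.5/SD)] / [1 − 2Φ(−3.5/SD)]. This is 0.6%, 3.9% and 7.1% for an SD of 1, 1.5 and 2 days, or about 2, 14 and 26 of 360 subjects. An even spread gives 1/7 = 14.3%, about 51. These are counts of Day 11 visits, not of wrong results.

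**Step 6. After the change.** With Week 1 as 2 to 10 and Week 2 as 11 to 21, every ±3-day range lies inside its own window. No other limit moves.

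**The case against.** **Shifted nominal days.** By the Section 3.7.1 count, a visit exactly 7 or 14 calendar days after the first dose is Study Day 8 or 15. Nominal days 8, 15, 29 and so on have midpoints 11.5, 22, 36, 50, 64 and 78. With tied days going to the later visit, these give upper limits 11, 21, 35, 49, 63 and 77, which is every limit in Table 3-1. Day 11 would then be an on-time Week 1 day (8 + 3) and too early for Week 2 (15 − 3 = 12). This stands as a possible origin of the limits. It does not remove the point, because the SAP prints Days 7 and 14 in both Table 3-1 and Section 4.2.1. Table 3-3 also splits Week 1 and Week 12 at 45/46, which fits (7+84)/2 = 45.5 and not (8+85)/2 = 46.5.

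**No stated midpoint rule.** This also stands. The HCV RNA limits in Table 3-2 (69/70 and 146/147) are not midpoints of 28, 84 and 168, which would be 56 and 126. A reader might infer that 11 is simply a slip for 10, but the document does not prove that. What it shows is that the nominal days, limits and tolerance do not agree. The 81-day threshold concerns exposure through Week 12 and only illustrates how the tolerance is counted.

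**The imputed failure depends on a reading.** Section 3.4.1 speaks of values before and after in time. Read literally, the Day 11 result is itself the preceding value. If it and the next value are < LLOQ, Week 2 is imputed as < LLOQ. Section 6.2.2 assigns values to windows before it mentions imputation, which favours the reading by visit but does not settle it.

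**The record is not lost.** This stands too. It remains in the listings, and Section 7.3.2.1 counts laboratory abnormalities at any postbaseline time.

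**Conclusion.** The inconsistency is real and minor. On the SAP's own nominal days and tolerance, Day 11 is a permitted Week 2 day placed in the Week 1 window, and no other permitted on-treatment day is misplaced. The effect is confined to single-value by-visit summaries. It requires a visit on Day 11 and no other record on Days 12 to 21.

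A reader might infer more, without support from the document:

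- That on-time Week 2 results are routinely turned into virologic failures. This needs a Week 1 value ≥ LLOQ taken as the preceding value, a Day 11 value < LLOQ, a last dose on or after Day 12, and no other Week 2 record.
- That a definite number of subjects is affected. The counts in the working rest on assumed scatter, and the number of wrong results cannot be derived.
- That SVR12 or its test is touched. SVR4, SVR12 and SVR24 use the posttreatment windows of Table 3-2. The by-visit on-treatment results carry exact confidence intervals but no hypothesis test.

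The conclusion assumes that the printed Days 7 and 14 are the intended ones.

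**What to change.** First confirm against the visit schedule that Days 7 and 14 are the intended nominal days.

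- **If they are:** in Table 3-1 set the Week 1 upper limit to 10 and the Week 2 lower limit to 11.
- **If Days 8, 15, 29 and so on were intended:** keep the limits and correct the nominal days in Table 3-1 and Section 4.2.1. Check Table 3-3, which also prints Days 7 and 84.

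The confirmation matters. If visits are in fact dated from Day 8, moving Day 11 to Week 2 would take an on-time Week 1 record out of its window and do the same harm in reverse.

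The cost of the first option is two numbers in one table and the matching programming constants. The second changes a column of nominal days and the selection rule that refers to it. Either should be done before the SAP is finalized.

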7.6. Electrocardiogram Results

A shift table of the investigators' assessment of ECG results at each visit compared with baseline values will be presented by region using the following categories: normal; abnormal, not clinically significant; abnormal, clinically significant; or missing. The number and percentage of subjects in each cross-classification group of the shift table will be presented. Subjects with a missing value at baseline or postbaseline will not be included in the denominator for percentage calculation. No inferential statistics will be provided.

A by-subject listing for ECG assessment results for all subjects will be provided by region, subject ID number and visit in chronological order.

A by-subject listing for clinically significant ECG assessment results will be provided by region, subject ID number and visit in chronological order.

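### The ECG windows leave some final ECGs out of the by-visit shift table, and the end-of-treatment ECG value has no lower bound and no assigned row

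*SAP*

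**What the plan says.** SAP section 3.7.2 sets the ECG cut-off: "ECG data collected up to the last dose date + 3 days are considered to be on-treatment data". The normal/abnormal reading "will be assessed for on-treatment data based on the visit windows as shown in" Table 3-3, which has two postbaseline windows: Week 1 (nominal Day 7, Days 2 to 45) and Week 12 (nominal Day 84, Day 46 onward with no upper limit). The note under the table places the postbaseline ECGs at Week 1 and at Week 12 or end of treatment, and says that the "end of treatment value will be the last available value on or prior to the last dose date + 3 days".

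Section 3.7.3 settles competition within a window: "The record closest to the nominal day for that visit will be selected". Categorical data follow the same rule; the worse value is preferred only among records from the same day.

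Section 7.6 specifies one ECG summary, a shift table: "ECG results at each visit compared with baseline values will be presented by region". Subjects with a missing baseline or postbaseline value are left out of the percentage denominator. Two by-subject listings follow, one of all ECG assessments and one of the clinically significant ones.

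Laboratory and vital sign data collected more than 3 days after the last dose go to a follow-up Week 4 window in Table 3-2 (follow-up Days 4 to 30). That table has no ECG columns.

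**The concern.** Only two postbaseline ECGs are scheduled, so the final one is the only tracing that reflects more than about a week of treatment. Three features of the text work against it.

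- The Week 1 window runs to Day 45. In a subject who stops early it can hold both the Week 1 ECG and the final ECG, and only one is kept.
- An ECG outside the 3-day cut-off has nowhere to go, unlike a laboratory or vital sign value.
- The end-of-treatment definition could supply a row for the final ECG, but it requires neither a postbaseline tracing nor one later than Week 1, and section 7.6 does not use it.

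At stake is whether the shift table shows the ECG status at the end of treatment for subjects who stopped early, and for some who completed.

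**Working it through.** No figure in the plan needs reproducing; the check applies its rules to constructed subjects.

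**Inputs.**
- Cut-off: ECG day ≤ last dose day + 3 (section 3.7.2).
- Windows: Days 2–45 and Day 46 onward (Table 3-3).
- Selection: smallest |ECG day − nominal day| (section 3.7.3).
- End-of-treatment value: latest ECG with day ≤ last dose day + 3 (note to Table 3-3).
- Visit tolerance: ±3 days, including the Week 12/ET column (Appendix 1).

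Each subject has ECGs on Day 1 and Day 7 plus one final ECG, except in the last line, where there is no Day 7 ECG.

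| Last dose | Final ECG | Gap | Week 1 row | Week 12 row | End-of-treatment value |
|---|---|---|---|---|---|
| Day 20 | Day 22 | +2 | Day 7 | none | Day 22 |
| Day 42 | Day 45 | +3 | Day 7 | none | Day 45 |
| Day 43 | Day 46 | +3 | Day 7 | Day 46 | Day 46 |
| Day 60 | Day 62 | +2 | Day 7 | Day 62 | Day 62 |
| Day 20 | Day 26 | +6 | Day 7 | none | Day 7 |
| Day 60 | Day 65 | +5 | Day 7 | none | Day 7 |
| Day 84 | Day 87 | +3 | Day 7 | Day 87 | Day 87 |
| Day 84 | Day 88 | +4 | Day 7 | none | Day 7 |
| Day 81 | Day 87 | +6 | Day 7 | none | Day 7 |
| Day 3 | Day 8 | +5 | none | none | Day 1 |

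**Displacement.** With last dose Day 20 and final ECG Day 22, the ECG is on treatment and inside Days 2–45. Its distance from nominal is |22 − 7| = 15 days, against |7 − 7| = 0 for the Week 1 ECG, so it is not selected. The worse-value rule does not apply, because the records are on different days. The final ECG would appear only as the end-of-treatment value, which has no row.

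**Exclusion.** The permitted Week 12 visit runs from Day 84 − 3 = 81 to Day 84 + 3 = 87. A last dose on Day 81 gives 81 − 1 + 1 = 81 days of exposure, which section 4.2.1 counts as exposure through Week 12: "the number of subjects who were exposed to study drug for at least 81 days". A visit on Day 87 is then 87 − 81 = 6 days after the last dose, beyond the cut-off. For last doses on Days 82 and 83 the largest in-tolerance gaps are 5 and 4 days, also beyond it. For Day 84 the gap is 3 days and the ECG is kept.

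**Missing lower bound.** In the last line the only ECG within last dose + 3 days is the Day 1 tracing. The end-of-treatment value is then the baseline itself, and a shift computed from it would be no change by construction.

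**The case against.** The strongest reply is that two of these effects depend on opposite readings of section 7.6. If the shift table has an end-of-treatment row, the punctual Day 22 ECG is shown there and is not lost. If it has none, carrying the Week 1 ECG forward never reaches the table. That is right, and the two harms should not be added together. It does not dispose of the point: the text does not say which reading holds, each reading has a defect, and an ECG beyond the 3-day limit is absent under both.

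The 3-day limit is also not an error in itself. HCV RNA, vital signs and laboratory data use it too, and Appendix 1 schedules no posttreatment ECG, which explains why Table 3-2 has no ECG window. This stands. The dropped Day 87 ECG needs an early last dose and a late visit together.

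A reader might infer more than the SAP supports:

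- That early stoppers' ECG findings are lost as a class. They are not. A final ECG from Day 46 onward and within 3 days of the last dose is kept as Week 12, even with a last dose on Day 43. The section 7.6 listings carry no stated on-treatment limit, so every ECG is still reported by subject.
- That the by-visit rows are biased toward no change. A missing cell leaves the denominator; it is not counted as unchanged. That bias could arise only in an end-of-treatment row filled by carry-forward.
- That the primary safety endpoint is affected. Section 7.1 defines it by AEs leading to permanent discontinuation, and section 7.2.5.1 counts any AE leading to premature discontinuation as treatment-emergent whatever its timing. ECG windows play no part in it.

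**Conclusion.** The point holds as a defect in the windowing rules for one descriptive table. The plan omits from the by-visit rows a final ECG on or before Day 45 when another ECG lies nearer Day 7. It also omits any ECG more than 3 days after the last dose, and it defines an end-of-treatment value that can precede the end of treatment by weeks and is tied to no output.

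The number affected cannot be computed, because the SAP gives neither the early-stop rate nor the delay to the final visit. Purely as an assumption, 1% to 5% of the 360 planned subjects would be 0.01 × 360 = 3.6 to 0.05 × 360 = 18. No test, efficacy result or primary safety result changes. The conclusion assumes that the windows are applied by date, as section 3.7.2 describes, and not by visit label.

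**What to change.** Amend the note to Table 3-3 and section 7.6 before the SAP is finalized:

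1. Add an end-of-treatment row to the shift table. Define its value as the last postbaseline ECG up to last dose + 3 days that was taken after the Week 1 visit record. Do not carry forward the Week 1 or baseline ECG; if no ECG qualifies, the value is missing.
2. Show ECGs collected after last dose + 3 days and up to 30 days in a separate row labelled posttreatment. This follows the treatment of laboratory and vital sign data in Table 3-2. These ECGs should not be called end-of-treatment values, since they would be off drug.

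The existing Week 1 and Week 12 rows can stay as they are. The change needs no new data or visits. Its cost is a few lines of SAP text and one or two sparse extra rows in an existing table.
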